The Cochlear™ Nucleus™ Cochlear Implant System consists of 1) the implanted device, CI24 RE (Contour Advance), and the CI422 (Slim Straight); 2) the externally worn Nucleus 6 speech processor; and 3) the Custom Sound fitting software used to program speech processors. Subject to change as commercial availability changes.

Med-EL Corporation

The Med-EL Maestro™ Cochlear Implant System consists of 1) the implanted device, the Concert™ Medium or Standard; 2) the externally worn Opus 2 speech processor and/or Rondo speech processor; and 3) the Maestro System fitting software used to program speech processors. Subject to change as commercial availability changes.

Participant Population

Thirty-seven to forty individuals with asymmetric hearing loss will participate at three to four U.S. CI centers. Participants will be sequentially recruited into the study to ensure a participant pool representative of the general adult population with asymmetric hearing loss. Participants will not be pre-selected based on age (other than being at least 18), gender or ethnicity. Each participant will meet the following inclusion and exclusion criteria:

Inclusion Criteria

- 18 years of age or older
- Proficient in English
- Have a desire for functional binaural hearing
- Have failed a previous HA treatment for asymmetric hearing loss (BiCROS or poor ear HA) or willing to complete a trial if necessary
- Willingness to comply with all study requirements
- Ability to provide informed consent
- Poor ear (ear to be implanted):
 - Pure-tone average (PTA) at .5, 1 and 2 kHz > 70 dB HL (hereafter referred to as severe to profound hearing loss – SPHL)
 - Aided word recognition score (CNC Word Test) at 60 dB SPL ≤ 30%

- Duration of SPHL \geq 6 months
- Onset of hearing loss \geq 6 years of age
- Better ear:
 - PTA at .5, 1, 2, 4 kHz of 40 to 70 dB HL
 - Currently using a HA
 - Aided word recognition score (CNC Word Test) at 60 dB SPL $>$ 40%
 - Stable hearing for the previous 1-year period. "Stable" is defined as thresholds that have not changed by more than 10 dB at 2 or more octave interval audiometric frequencies

Exclusion Criteria

- Medical condition that contraindicates surgery
- Actively using an implantable device in the ear to be implanted
- Known cochlear malformation or obstruction that would preclude full insertion of the electrode array in the ear to be implanted
- Hearing loss of neural or central origin

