A research study team member, either the surgeon or audiologist working with the patient, will identify potential participants. If a patient indicates interest in participation, the surgeon or audiologist will have a detailed conversation about the study procedures, purpose, schedule, and time commitments and provide a copy of the consent document. Potential participants will have the opportunity to take the consent document home to read and discuss with family and friends and will be encouraged to contact the surgeon and/or the audiologist if there are questions. Study team members will ensure that the potential participant is aware of all aspects of cochlear implantation as well as study expectations, the surgical procedure, and the post-implant study schedule. When informed consent is obtained, each section of the consent form will be reviewed and the potential participant will be given an opportunity to ask questions. Individuals who are still interested in participating will sign and date the consent form. Several aspects of the individual's participation will be highlighted during the consent process: (1) participation is voluntary; (2) the participant can withdraw from the study at any point for any reason; and (3) the participant will receive appropriate clinical care whether or not they participate in the study. The participant will be given a copy of the signed consent document.

Summary of Study Schedule

| Activity/Measure | Condition | Candidacy Evaluation | Pre-Implant Testing | Initial Stim | Post-Implant 3 mo | Post-Implant 6 mo | Post-Implant 9 mo | Post-Implant 12 mo |
|--|---------------------------|----------------------|---------------------|--------------|-------------------|-------------------|-------------------|--------------------|
| Informed Consent | | X | | | | | | |
| Air Conduction Thresholds | Each ear alone | X | | X | X | X | X | X |
| Bone Conduction Thresholds | Each ear alone | X | | | | | | |
| Sound Field Thresholds | Each ear alone | X | X | | X | X | X | X |
| CNC Words @ 60 dB SPL | Each ear alone | X | | | X | X | X | X |
| | Both ears together | | X | | X | X | X | X |
| AzBio Sentences @ 60 dB SPL | Poor ear alone | | X | | X | X | X | X |
| AzBio Sentences @ 50 dB SPL | Better ear alone | | X | | X | X | X | X |
| | Both ears together | | X | | X | X | X | X |
| AzBio Sentences @ 60 dB SPL +8 dB SNR | Better ear alone | | X | | X | X | X | X |

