Participants will have their HAs assessed to ensure proper functioning and adequate amplification prior to testing. The American National Standard Institute S3.22-2009 for electroacoustic assessment will be used to ensure proper HA functioning. Amplification will be evaluated using real-ear measures with the AudioScan Verifit™ (or equivalent) system with speech stimuli for input levels of 50, 60 and 70 dB SPL. The evaluation will be based on the National Acoustic Laboratories' nonlinear fitting procedure, version 2 (NAL-NL2). If the participant's HAs do not meet NAL-NL2 targets within ± 10 dB from 500-4000 Hz, the HAs will be re-programmed until targets are met. If the HAs cannot be adjusted to meet targets, the participant will be fit with clinic loaner HAs. If the severity of the hearing loss or tolerance issues prohibit amplification at the prescribed levels, the HA will be programmed as close as possible to NAL-NL2 targets.

Aided, FM Tone Sound Field Threshold levels

Aided, FM tone threshold levels will be obtained in the sound field for each ear at 250, 500, 1000, 2000, 3000, 4000, and 6000 Hz. When testing the poor ear, the better ear will be plugged and muffed (Howard Leight Pre-Shaped Foam Earplug and Howard Leight Hearing Protection Thunder T1 earmuff) (Howard Leight, 2014a, b). Based on pilot data from Washington University School of Medicine, the plug and muff provided an attenuation average of 48 dB for frequencies 250 – 8000 Hz.

CNC Word Recognition Testing

Two list of the CNC word test will be given to participants at 60 dB SPL in two listening conditions, 1) HA in the better ear only and 2) HA in the poor ear only. When testing the poor ear, the better ear will be plugged and muffed. Testing will determine if the participant meets inclusion criteria.

Alternative Therapy Assessment

Participants who have not previously failed a poor ear HA or BiCROS HA trial will be fit with one of those two HA options. The audiologist will determine which HA to fit based on the participant's hearing loss and preferences. After at least 1 to 2 weeks of use, the

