participant will return to the center and complete an evaluation. Performance will be compared (using measures listed below) between the better ear HA-alone condition and the bilateral or BiCROS HA condition. If performance is better in the bilateral or BiCROS HA condition versus the better ear HA-alone condition, and the participant prefers the alternative therapy, the participant will not continue in the study. For participants who do continue in the study, these measures will not need to be repeated at the Pre-Implant Testing visit.

Sentence testing

Two lists of AzBio sentences will be administered at 60 dB SPL in 4-talker babble at +8 dB SNR.

Localization

CNC words will be presented through the eight loudspeaker array at a roved level of 65 dB SPL (± 6 dB).

Candidacy Determination

The Investigator is required to submit the pre-operative candidacy evaluation CRFs for review by the Sponsor once the candidacy evaluation (when necessary, including the alternative therapy assessment) is complete. The information collected will be reviewed by the Sponsor, and a written approval or disapproval will then be provided to the Investigator. The Pre-Implant Candidacy Evaluation should take place within 4 months of surgery. Portions of the Candidacy Evaluation will be reassessed if more than 4 months have elapsed prior to the surgery date.

Pre-Implant Study Testing

The duration of this testing will be approximately 4 hours and will be completed in 1-2 visits. Pre-Implant study testing will be completed in the following three conditions: a HA in the better ear only, a HA in the poor ear only, and bilateral HAs.

Hearing Aid in the Better Ear

The participant will wear the HA and HA settings verified during the candidacy evaluation. If a loaner clinic HA was needed during the pre-implant candidacy evaluation, the participant will have worn this HA for at least 2 weeks prior to the pre-implant study testing. Participants will continue to use this HA for the remainder of the study.

Aided, FM Tone Sound Field Threshold Levels

Aided FM tone sound field levels will be obtained at 250, 500, 1000, 2000, 3000, 4000 and 6000 Hz

Sentence testing

Two lists of AzBio sentences will be administered in quiet at a soft level of 50 dB SPL. Two lists of AzBio sentences will be administered at 60 dB SPL in 4-talker babble at +8 dB SNR.

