A record of all adverse events will be kept. No formal statistical hypothesis will be tested. The primary safety endpoint will be 6 months post-implant. Adverse event information through 6 months post-implant will be summarized by event type, severity/seriousness, and whether related to the device and/or implant procedure.

Efficacy

The primary study objective is to obtain preliminary efficacy data in adults with asymmetric hearing loss who receive a CI in the poor hearing ear and maintain a HA in the better hearing ear. Efficacy is defined as post-implant improvement in the poor ear with a CI compared to pre-implant with a HA. Measures are sound field threshold levels and CNC monosyllabic words in quiet.

A secondary objective is to obtain efficacy data related to bimodal hearing. Efficacy is defined as post-implant improvement (CI in poor ear + HA in better ear) compared to the pre-implant best-aided condition (either HAs in both ears, or a HA in the better ear alone for adults with no aidable hearing in the poor ear). Measures are sound localization, speech recognition in noise, speech recognition at soft presentation levels, perceived hearing handicap, and reported quality of life.

Sample Size Justification

The primary efficacy endpoint is change in CNC performance from pre-implant to post-implant, with most of the gain expected to be achieved by 6 months. A clinically meaningful change on the CNC test is .10. In our past research we have found CNC standard deviations that range from .06 to .24. Assuming a correlation between repeated measures of .5 (typical in our work) these values translate into standardized mean differences (Cohen's *d*) ranging from .42 to 1.67. At the minimum effect size, a sample size of 37 is necessary for power of .80, the common standard (Cohen and Cohen, 1983; Keppel, 1991; Cohen, 1992). As indicated, the planned sample size will provide adequate to excellent power to detect clinically meaningful differences. Up to 40 participants will be enrolled to allow for attrition.

Note that the analyses described later will often be more complex than the simple approach used here for power calculations (a dependent means t-test), often involving change over longer periods of time, examining nonlinearity in the change profiles, and including additional predictors (e.g., patient characteristics). The impact of these modifications will generally be to increase power by including additional measures that

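### The poor-ear CNC score that decides eligibility is also the only planned baseline for the primary CNC change, so regression to the mean can inflate the gain modestly

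*Combined protocol and SAP*

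**What the plan says.** Sample Size Justification states: "The primary efficacy endpoint is change in CNC performance from pre-implant to post-implant". The primary objective (Study Objectives; Efficacy) compares the poor ear with a CI against the same ear with a HA, and names two measures: "Measures are sound field threshold levels and CNC monosyllabic words in quiet".

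Inclusion Criteria, poor ear, requires "Aided word recognition score (CNC Word Test) at 60 dB SPL ≤ 30" percent. Under Pre-Implant Candidacy Evaluation, CNC Word Recognition Testing, two lists are given to each ear separately, and "Testing will determine if the participant meets inclusion criteria". The Summary of Study Schedule row reads "CNC Words @ 60 dB SPL | Each ear alone | X | | | X | X | X | X": a mark at candidacy, none at Pre-Implant Testing or initial stimulation, then 3, 6, 9 and 12 months. Pre-Implant Study Testing, Hearing Aid in the Poor Ear, lists sound field thresholds and AzBio at 60 dB SPL, but no CNC. Candidacy Determination allows unspecified parts of candidacy to be reassessed if surgery is more than 4 months later.

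On aids, Verification of Hearing Aids says: "If the HAs cannot be adjusted to meet targets, the participant will be fit with clinic loaner HAs". No wear period is stated before the candidacy CNC test. The one statement on loaner wear is under Hearing Aid in the Better Ear at the later visit: "the participant will have worn this HA for at least 2 weeks prior to the pre-implant study testing".

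**The concern.** A participant whose true aided score is a little above 30% enters after an unlucky test. One whose true score is a little below is kept out by a lucky test. Among those enrolled, the selecting score therefore understates the true aided score on average, and a retest would rise with no treatment. The trial has no control arm to absorb that rise, and Data Analysis provides no correction for it.

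The candidacy evaluation can be done in one visit, so a loaner or re-programmed poor-ear aid could be scored on the day it is fitted, whereas the CI is scored after 3 to 12 months of use. Any such effect would act in the same direction.

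The reported gain matters beyond this trial. Study Design says the results will help set the baseline conditions and final sample size of a Phase III trial.

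**Working it through.** **Plan's own figure.** With correlation .5, SD of change = SD × √(2(1 − .5)) = SD. So d = .10/.24 = .42 and .10/.06 = 1.67, as stated. For a paired t-test at d = .42 and power .80, N = 37 reproduces at one-sided alpha .05 (power .805). Two-sided .05 needs 47, and power at 37 is .70. The plan states neither alpha nor sidedness; two-sided .05 is assumed below.

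**Test error.** Two 50-word lists give 100 words. SE = √(p(1 − p)/100), which is 3.0, 4.0 and 4.6 points at true scores of 10%, 20% and 30%.

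**Regression to the mean.** True aided scores p are drawn from an assumed Beta distribution, session noise of assumed SD 0, 5 or 8 points is added, and the observed score is Binomial(100, p)/100. Those at or below .30 are kept and an independent retest is drawn with no treatment effect (2,000,000 draws per row). Bias = mean retest − mean selecting score. The false-positive rate is the two-sided 5% paired t-test at n = 37, with noncentrality √37 × bias/SD of change, using each row's own SD. The last column uses the plan's sizing SD of .24.

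| Assumed true scores | Session SD (points) | Bias (points) | SD of change (points) | False-positive rate | Rate at SD .24 |
|---|---|---|---|---|---|
| Beta(0.5, 3) | 0 | 0.20 | 3.7 | 6.2% | 5.0% |
| | 5 | 0.46 | 7.1 | 6.8% | 5.1% |
| | 8 | 0.92 | 9.7 | 8.7% | 5.6% |
| Beta(1, 4) | 0 | 0.37 | 4.5 | 7.7% | 5.1% |
| | 5 | 0.82 | 7.8 | 9.5% | 5.5% |
| | 8 | 1.61 | 10.6 | 14.5% | 6.8% |
| Beta(1, 2.5) | 0 | 0.50 | 4.7 | 9.7% | 5.2% |
| | 5 | 1.11 | 8.0 | 12.9% | 5.9% |
| | 8 | 2.09 | 10.9 | 20.5% | 8.1% |
| Beta(2, 5) | 0 | 0.74 | 5.2 | 13.3% | 5.4% |
| | 5 | 1.62 | 8.5 | 20.5% | 6.8% |
| | 8 | 2.94 | 11.4 | 33.2% | 11.2% |

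**Sensitivity to where true scores lie.** With true scores near floor (mean 5, SD 6) the bias from test error alone is 0.02 points. With true scores clustered at the cut (mean 30, SD 6) it is 2.0 points from test error alone and 3.8 with session SD 5. In the extreme case where every true score is 30%, these become 3.3 and 5.0.

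**Carry-over to planning.** If 1 point of an observed 10-point gain were artefact, the true d at SD .24 would be .09/.24 = .375 rather than .417. One-sided power at 37 falls from .80 to .72, and the N for 80% power rises from 38 to 46.

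**Aid experience.** No calculation is possible, because the documents give no figure for the effect of wear time on CNC.

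**The case against.** The size is the main ground for resistance. The distributions and session SDs are assumptions with no source in the documents. The poor ear must also have a PTA above 70 dB HL and at least 6 months of severe to profound loss, and the plan expects some participants to have no aidable hearing there. Many scores may lie near floor, where the effect vanishes. This stands, and it keeps the estimate to a range.

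The trial seeks preliminary efficacy data and states no success threshold, so a false-positive rate under exactly zero gain is a limited measure of harm. That also stands. The bias in the estimate matters more than the test.

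Three stronger readings are tempting but unsupported:

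- A reader might infer that the primary objective has no other baseline. Sound field thresholds, the second primary measure, are taken at both candidacy and Pre-Implant Testing. The possible reassessment after 4 months is not a planned second CNC baseline, since the parts to be repeated are not named.
- A reader might pair a 2-point bias with the plan's lowest SD of .06 and obtain a false-positive rate of 51%. In the table, a bias of 2 points or more arises only where the SD of change is about .11, because the session noise that creates the bias also widens the change. The matched rates there are 20.5% and 33.2%.
- A reader might infer that the two ears' aid-wear passages contradict each other and that reconciling them would mend the baseline. The 2-week statement concerns Pre-Implant Study Testing and covers the candidacy CNC test of neither ear. The absence of a stated wear period is a gap, and its effect is possible for some participants rather than shown. Some will already have used a poor-ear aid. The 1-2 week alternative-therapy trial does not close the gap, since it may use BiCROS and is followed by AzBio in noise and localization, not CNC.

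**Conclusion.** The point holds for CNC, at modest size. The selecting score is the only planned poor-ear CNC baseline, and the direction of the regression effect is upward for the gain. Under the assumed distributions it is 0.2 to 0.7 points from test error alone and 0.5 to 2.9 points with session SD 5 to 8, against a 10-point meaningful change. It is near nil at floor and larger if true scores cluster at 30%. The matching two-sided false-positive rate at n = 37 is about 6 to 33%, or 5 to 11% at SD .24, with alpha and sidedness assumed. The documents do not support reading the expected implant gain as an artefact of selection. A newly fitted aid may add to the bias in some participants, by an amount that cannot be estimated. The change is worth making because it is cheap and the estimate is meant to inform a Phase III design.

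**What to change.** Add two CNC lists at 60 dB SPL, poor-ear HA alone, to Pre-Implant Study Testing, where that ear is already tested with the better ear plugged and muffed, and mark the schedule accordingly. Name that score as the CNC baseline for the primary analysis, and use the candidacy score for eligibility only. If errors at the two visits are independent, this removes the regression effect by construction. It does not by itself settle aid experience, because no wear period is stated for the poor ear at that visit either. Recording how long the poor-ear aid had been worn at each CNC test would let readers judge it.

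If no test can be added, report the poor-ear AzBio 60 dB SPL change as supporting evidence: its baseline comes from the later visit and is not used for selection.

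Cost: two more 50-word lists in a visit of about 4 hours, slightly more exposure to the 10 available lists, and a slightly smaller reported gain.

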The Participant Interview Form will be completed by the investigator after questioning the participant. This will provide information regarding tinnitus, dizziness, medications, the incision/implant site, and other relevant information.

Participants' take-home speech processor programs

The audiologist at each center will provide a de-identified copy of the speech processor programs. This will document relevant information regarding the parameters used by the participant with their speech processor.

Aural Rehabilitation

All participants will be encouraged by their audiologist to practice daily for 15-30 minutes listening with their CI only for at least the first 6 weeks of implant use and then 3 times a week for an additional 6 weeks. During practice, participants can listen with their CI through direct audio input to their CI or can listen through the CI alone by plugging the better hearing ear with an earplug. Each participant will be given a list of practice materials available for use on a computer, tablet, smart phone or through a CD player.

Post-Implant Study Testing (3, 6, 9 and 12 months after Initial Stimulation)

The duration of each session will be approximately 4-5 hours and will be completed in 1-2 visits. Audiometric, speech recognition, localization, self-assessment, speech processor program, and adverse event data will be obtained at each of the four post-implant test intervals. Post-implant test intervals should occur within a \pm 30 day window around the target test date. Speech recognition and localization data will be obtained in multiple listening conditions as listed below.

Unaided Audiometric Threshold Levels*

Air conduction thresholds using insert earphones will be obtained for each ear at 250, 500, 1000, 2000, 3000, 4000, 6000 and 8000 Hz. Masking will be used when appropriate

*If unaided audiometric testing at the initial stimulation reveals no response at each frequency in the CI ear, unaided audiometric testing in the CI ear does not need to be done at each post-implant test session.

Hearing Aid in the Better Ear

Verification of Hearing Aid

Each hearing aid will be checked for proper function and sound quality (e.g., listening check, electroacoustic analysis, patient report).

Aided, FM Tone Sound Field Threshold Levels

Aided FM tone sound field levels will be obtained at 250, 500, 1000, 2000, 3000, 4000 and 6000 Hz.

CNC Word Test

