HUI3: The HUI3 will be completed by the participant at the 6-month post-implant study visit. The HUI3 will provide a post-implant measure of the participant's overall health related quality of life.

SSQ: The SSQ will be completed by the participant at the 6-month and 12-month post-implant study visits. The SSQ will provide a measure of the participant's perceived hearing ability in daily life with the CI and HA. The SSQ will be anchored for each of the post-implant test intervals; that is, participants will see how each question was answered at their previous test interval.

GBI: The GBI will be completed by the participant at the 6-month post-implant study visit. The GBI will document how the CI has affected the participant's health status and overall quality of life.

SADL

The SADL will be completed by the participant at the 6-month post-implant study visits. The SADL will provide a post-implant measure of the participant's satisfaction of the cochlear implant.

Participant Interview Form

The Participant Interview Form will be completed by the investigator after questioning the participant. This will provide information regarding tinnitus, dizziness, medications, the incision/implant site, and other relevant information.

Participants' speech processor programs used for testing

The audiologist at each center will provide a de-identified copy of the speech processor programs. This will document relevant information regarding the parameters used by the participant with their speech processor.

Spouse/Significant Other – Post-Implant Questionnaires

CPHI

The CPHI will be completed by the participant's spouse/significant other at the 6-month post-implant study visit. The CPHI will provide a post-implant measure of the participant's communication in everyday life from the perspective of the spouse/significant other.

HII-SOP

The HII-SOP will be completed by the participant's spouse/significant other at the 6-month post-implant study visit. The HII-SOP will provide a post-implant measure of the perceived impact of the participant's hearing loss on the participant's spouse/significant other.

Safety

A secondary objective of this study is to obtain data regarding the safety of cochlear implantation in adults with asymmetric hearing loss who receive a CI in the poor hearing ear and maintain a HA in the better hearing ear. The safety evaluation will be based on the number, type and degree of all adverse events.

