- Copies of all case report forms submitted to the Sponsor.
- Site Delegation Signature Log.

All study-related records must be maintained for at least two years after study closure. The Sponsor will notify investigators at each site when records are no longer needed. The investigator will not discard any records without notifying the Sponsor.

Study Report and Publication

Neither the complete nor any part of the results of the study carried out under this protocol, or any of the information provided by the sponsor site for the purposes of performing the study, will be published or passed on to any third party without the consent of the Sponsor (via the study Principal Investigator, [name]). Any investigator involved with this study is obligated to provide the Sponsor with complete test results and all data derived from the study.

At completion of the study, the compiled data will be analyzed and results shared with investigators from the investigational sites. Likewise prior to publication of results, the investigators from the investigational sites will be provided a copy of the accepted publication manuscript.

Adverse Events

Adverse Event (AE)

An AE is any unexpected medical occurrence or worsening of a pre-existing medical condition following implantation and exposure to the device, regardless of whether the AE is related to the surgery or device.

Adverse events (AEs) that occur during this study may be associated with the CI surgery, including AEs from general anesthesia, or specifically associated with the device use. An AE will be deemed device-related when, in the judgment of the study site's Primary Investigator, there is a logical connection between the device use and the event, above and beyond the study procedure itself.

Serious Adverse Event (SAE)

A SAE is any unexpected medical occurrence which:

- Results in death
- Is life-threatening
- Requires in-patient hospitalization for more than 24 hours or prolongation of hospitalization which is not specifically required by the protocol
- Results in permanent impairment of a body function or permanent damage to a body structure
- Requires medical or surgical intervention to preclude permanent impairment of a body function or permanent damage to a body structure

Unanticipated Adverse Device Effect (UADE)

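### Unaided thresholds of the implanted ear are collected through 12 months but enter no stated analysis, and the AE-only safety evaluation has no rule for coding a threshold loss

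*Combined protocol and SAP*

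**What the plan says.** **What is measured.** The Summary of Study Schedule lists air-conduction thresholds, each ear alone, at candidacy, initial stimulation and 3, 6, 9 and 12 months. The text under Post-Implant Study Testing agrees: "Air conduction thresholds using insert earphones will be obtained for each ear at 250, 500, 1000, 2000, 3000, 4000, 6000 and 8000 Hz". There are two exemptions. Under Initial Stimulation, a poor ear with no response at any frequency before surgery need not be tested again. Under Post-Implant Study Testing: "If unaided audiometric testing at the initial stimulation reveals no response at each frequency in the CI ear", then "unaided audiometric testing in the CI ear does not need to be done at each post-implant test session".

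**Who can have hearing to lose.** For the ear to be implanted, the Inclusion Criteria ask for "Pure-tone average (PTA) at .5, 1 and 2 kHz > 70 dB HL" and an aided CNC score of at most 30%. Measurable hearing before surgery is therefore possible but not required.

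**What safety rests on.** The Safety section says "The safety evaluation will be based on the number, type and degree of all adverse events". It adds "No formal statistical hypothesis will be tested" and "Adverse event information through 6 months post-implant will be summarized by event type, severity/seriousness".

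**How events are defined.** An AE is either an unexpected medical occurrence or the worsening of a condition already present, after implantation and exposure to the device. An SAE is an unexpected occurrence that meets one of a list of criteria, among them: "Results in permanent impairment of a body function or permanent damage to a body structure". Investigator Responsibilities requires AEs to be recorded even when the consent form names them as risks.

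**The concern.** A change in the unaided thresholds of the operated ear is a direct measure of what the procedure did to the hearing that was there. The trial collects it serially, but the plan sends it nowhere. The safety result then depends on whether an investigator turns an audiogram into an adverse event, with no decibel criterion to guide that step and with definitions that do not settle how serious the event is.

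Safety is a stated secondary objective. The results are also meant to inform a later pivotal trial, including its inclusion and exclusion criteria. Hearing lost in the operated ear bears directly on how much residual hearing such criteria should allow.

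**Working it through.** **1. Is there a stated use for the thresholds?**

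- Study Objectives and Efficacy: the primary measures are sound field thresholds and CNC words. The secondary measures are localization, speech in noise, soft speech, perceived handicap and quality of life. Unaided thresholds are not named.
- Safety: adverse events only.
- Data Analysis: a general growth-curve model with CNC as its example outcome, plus simpler analyses at single time points. Unaided thresholds are not named.
- Sound field thresholds do not stand in for them. Before surgery they are taken in the poor ear through the HA, and afterwards through the CI. They can improve while unaided hearing is lost.

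**2. Would the adverse-event route capture a loss in a uniform way?**

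| Element | Direction |
|---|---|
| AE definition, worsening of an existing condition | towards recording |
| Recording rule for risks named in the consent form | towards recording |
| SAE criterion of permanent impairment | towards serious |
| SAE lead-in limited to *unexpected* occurrences | away from serious, if a site regards the loss as expected |
| Decibel criterion for a threshold shift in the implanted ear | none |
| Participant Interview Form, used to help find AEs | names tinnitus, dizziness, medications and the implant site, not hearing |
| AE form items | seriousness as yes or no, with no severity grade, although Safety promises a summary by severity |

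The only threshold-change rule in the protocol (more than 10 dB at two or more frequencies) is an eligibility rule for the better ear. The planned AE summary stops at 6 months, while thresholds run to 12. With three to four sites, the AE wording leans towards recording, but nothing fixes when a shift counts or whether it is serious.

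**3. How large could the effect be?** The plan gives no safety figure to reproduce: no rate of loss and no share of ears with measurable hearing. What follows is an assumed range. The 37 is the planned sample size, used only as a count of implanted ears. Let m be the share with measurable hearing at baseline and q the share of those who lose it.

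Ears at risk = 37 × m; ears with loss = 37 × m × q, both rounded. Intervals are exact (Clopper-Pearson) 95%, with ears at risk as the denominator.

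| m | q | Ears at risk | Ears with loss | Loss among ears at risk (95% CI) | If none is coded |
|---|---|---|---|---|---|
| 50% | 10% | 19 | 2 | 10.5% (1.3 to 33.1) | 0/19 (0 to 17.6%) |
| 50% | 70% | 19 | 13 | 68.4% (43.4 to 87.4) | 0/19 (0 to 17.6%) |
| 100% | 10% | 37 | 4 | 10.8% (3.0 to 25.4) | 0/37 (0 to 9.5%) |
| 100% | 70% | 37 | 26 | 70.3% (53.0 to 84.1) | 0/37 (0 to 9.5%) |

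On these assumptions, 2 to 26 of 37 participants would be affected. The last column is the limiting case in which no site logs the loss; the AE wording makes that the less natural reading. The AE-versus-SAE split of the same participants can fall anywhere from none serious to all serious.

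**4. The retest exemption.** It applies only after no response at every frequency has been recorded at initial stimulation, so the total loss is already in the data. However, no rule says how such an ear is scored at 6 or 12 months. A table built from available values would leave it out, so any threshold summary needs that rule.

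**The case against.** The strongest reply is that the event definitions already work. The worsening limb of the AE definition is not limited to unexpected events, and acknowledged risks must still be recorded. A site that logged nothing would be going against the plainer reading. Safety is descriptive in a preliminary single-arm study, the DSMB reviews adverse events and factors affecting participant safety, and the primary comparison shows the net functional result in the same ear with HA before and CI after.

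Much of this stands. A reader might infer that the plan lets the loss vanish from the record. The documents do not support that: they lean towards recording it as an AE. What remains is that no shift is defined as an event and seriousness is unsettled. The functional comparison does not show acoustic hearing lost, and a descriptive objective still needs its measured outcome described.

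A reader might also infer that many participants are irreversibly harmed. No passage gives a rate or says that a loss is permanent. Nor can a loss rate be applied to all 37 ears, because the protocol expects some poor ears to have no response before surgery.

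Finally, a reader might infer that the retest exemption biases the results. It would do so only in a summary of available values, and the plan specifies no such summary.

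**Conclusion.** The point holds as a gap in the safety analysis that should be closed. Unaided thresholds of the implanted ear are collected serially and no stated analysis uses them. Safety rests on adverse events alone, and the definitions leave open when a threshold loss is an event and whether it is serious. Followed as written, the plan can produce a safety result that omits measured hearing loss in the operated ear or classifies it differently by site.

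This conclusion rests on the text and needs no assumption about rates. The size is unknown; the range of 2 to 26 of 37 rests entirely on assumed shares (50 to 100% with measurable hearing, 10 to 70% of those losing it).

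**What to change.** Add to Safety a descriptive summary of the change in unaided air-conduction thresholds of the implanted ear, from candidacy to initial stimulation, 6 and 12 months:

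- Among ears with measurable hearing at baseline, which form the denominator, report the number with no response afterwards, with an exact 95% CI, and the change in the .5, 1 and 2 kHz average. State how many ears had no response at baseline and so are outside the denominator.
- Score no response at the audiometer limit, with that limit written down for each frequency. The documents do not give it.
- Carry a no response at every frequency at initial stimulation forward as loss, not as missing. Where a site retested anyway, use the measured value.
- Report the table for every participant, whether or not the site logged an AE or SAE.

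Separately, reconcile the AE and SAE definitions with the recording rule under Investigator Responsibilities, so that all sites code a threshold loss in the same way.

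The cost is protocol and SAP wording and one extra table. No visit or test is added, because the data are already scheduled. The safety profile may look less favourable.
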